**PROTOCOL AMENDMENT 8 SUMMARY OF CHANGES**

This eighth amendment to the protocol for Study PVO-1A-202 was finalized on 30 November 2020.

Location/Section Number	Change	Rationale
Major changes that affected the clinical conduct of the study:		

Protocol Synopsis                      Tables 1 and 4                      Section 1.1.3.2 Clinical Data                      Section 3.1 Overview of Study Design                      Section 3.2 Study Rationale                      Section 7 Study Procedures and Assessments                      Section 2.3 Secondary Objectives                      Section 5.7 Subject Withdrawal or Early Termination                      Section 9.1.10 Follow-up of Adverse Events and Serious Adverse Events
	
Part D was added for skeletally immature subjects who stopped taking study drug for any reason before completion of Part A/B/C. Part D includes yearly visits for up to a 2-year follow-up period following last dose. No dosing will occur during Part D.
 
Assessments obtained in Part D include yearly linear height, knee height, weight, physical exam, vital signs, radiographic assessments of the knee and hand/wrist, low-dose WBCT imaging excluding head, adverse events, and concomitant medications.
 
Participation in Part D will continue as long as subjects remain skeletally immature.
 
The up to 2-year period would begin the last day the subject stopped receiving study drug in Part A/B/C. The total duration of participation in Part C and Part D, is a maximum of 4 years.
 
Secondary objective added for Part D to monitor off treatment longer-term safety in skeletally immature subjects off treatment.
 
Safety will be summarized for Part D.
	
To implement safety measures based on DMC recommendations given the serious identified risk of premature physal closure. Part D is being implemented to ensure that assessments of safety are offered for up to 2 years to subjects who were skeletally immature at the time they stopped taking study drug for any reason before completion of Part A/B/C. A 2-year follow up is an adequate timeframe to assess growth and physal changes off palovarotene treatment. Preliminary data suggest that the risk of premature epiphyseal fusion is higher in subjects with open epiphyseal growth plates who have received the flare-up dosing regimen. A 2-year follow up is an adequate timeframe to assess growth and epiphyseal changes off palovarotene treatment.
 
To allow for provision of study medication until commercial availability.


Protocol Synopsis                      Section 3.1 Overview of Study Design                      Section 3.2 Study Rationale                      Section 5.1 Study Population (Adult and Pediatric Cohorts – Part B)                      Section 7.7 Temporary Measures (Procedures Related to COVID-19 Pandemic)
	
As of 04Dec2019 all subjects < 14 years of age were required to interrupt study drug due to a partial clinical hold placed on the palovarotene clinical development program by the US FDA. Treatment will subsequently not be restarted in children <14 years of age.
	
As a consequence of FDA Partial Clinical Hold subjects remained off treatment for a prolonged period of time. As such a significant gap in dosing occurred which would render any further data to inform additional benefit/risk uninterpretable in this patient population. Part D was added to ensure continued collection of safety data off treatment.

Protocol Synopsis                  Tables 1 and 2                  Sections 2.3 and 4.2                  Secondary Endpoints                  Section 3.1 Overview of Study Design                  Section 7 Study Procedures & Assessments                  Section 7.2.2 Physical Examination                  Section 7.2.3 Body Weight and Linear Growth                  Section 7.2.4 Vital Signs                  Section 7.2.5 Electrocardiogram                  Section 7.2.6 Clinical Laboratory Test                  Section 7.3.1 Columbia-Suicide Severity Rating Scale                  Section 7.3.2 Knee and Hand/Wrist Radiographs                  Section 7.4 Efficacy Assessments                  Section 7.4.1 Low-dose Whole Body Computed Tomography                  Section 7.4.2 FOP-Physical Function Questionnaire                  Section 7.4.3 PROMIS Global Health Scale                  Section 7.4.4 Cumulative Analogue Joint Involvement Scale
	
In Part C, subjects may continue on the study for up to an additional 12 months.
	
To allow for provision of study medication until commercial availability.

Section 7.3.3 Bone Safety Management Plan
	
Added assessments for spinal health carried out on low dose WBCT scans collected in the study.
	
Emerging data from PVO-2A-201 trial in the multiple osteochondroma indication has suggested a potential effect of PVO on bone mineral accrual. As such, assessments were added to further characterize this risk in subjects with FOP.


Section 7.1 Screening, Recruitment, and Informed Consent                  Section 7.7 Temporary Measures (Procedures Related to the COVID Pandemic)
	
Integrated protocol amendment 7 addendum previously created to describe temporary measures applied during the COVID pandemic. Additional update to these temporary measures to clarify that radiographic assessments are required for subjects <math>\geq 14</math> years (who were skeletally immature at their last assessment) as part of the minimal safety procedures
	
To integrate protocol amendment 7 for addendum. To assess skeletal maturity in subjects <math>\geq 14</math> years re-initiating treatment in order to ensure appropriate safety follow up as well as determine if weight-based dosing is required.

	prior to re-initiation of palovarotene.	
Changes that did not affect the clinical conduct of the study:		
Table 3	Removed ECG row that was included in error; correcting table and footnotes.	Integration of administrative change from protocol amendment 7 addendum.
Section 7.6	Added DMC language.	Clarifying DMC oversight
Section 9.1.10 Follow up of Adverse Events and Serious Adverse Events	Collection of SAE reports, including deaths, will continue until 30 days past end of study.	Clarification of end date of collection of SAE, including death reports.
General	Corrected minor errors and formatting irregularities.	To provide a consistent presentation.

**PROTOCOL SYNOPSIS**

Title	A Phase 2, Open-Label Extension, Efficacy and Safety Study of a RAR $\gamma$ -Specific Agonist (Palovarotene) in the Treatment of Preosseous Flare-ups in Subjects with Fibrodysplasia Ossificans Progressiva (FOP).
Sponsor	Clementia Pharmaceuticals Inc.
Objectives	
Primary Objective
 
 
To evaluate the safety and efficacy of different palovarotene dosing regimens in subjects with FOP. Efficacy will be based on the ability of palovarotene to prevent the formation of new heterotopic ossification (HO) as assessed by low-dose whole body computed tomography (WBCT) scan, excluding head.
 
 
Secondary Objectives
 
 
To evaluate the effect of palovarotene on range of motion (ROM) as assessed by the Cumulative Analogue Joint Involvement Scale (CAJIS) for FOP.
 
To evaluate the effect of palovarotene on physical function using age-appropriate forms of the FOP-Physical Function Questionnaire (PFQ).
 
To evaluate the effect of palovarotene on physical and mental health using age-appropriate forms of the Patient Reported Outcomes Measurement Information System (PROMIS) Global Health Scale.
 
To evaluate the pharmacokinetics of palovarotene.
 
 
Secondary Objective (Part D)
 
 
To implement safety measures based on DMC recommendations in order to ensure that assessments of safety continue for up to 2 years post last dose of study treatment for skeletally immature subjects.
 

Study Design	
A Phase 2, multicenter, open-label study that will explore different dosing regimens of palovarotene in adult and pediatric subjects with FOP.
 
Part A includes all data obtained prior to Amendment 3 (dated 10 March 2016) during which pediatric and adult subjects successfully completing Study PVO-1A-201 were enrolled and followed for up to 36 months. Any subject experiencing an eligible flare-up under Part A received treatment with open-label palovarotene at a dose of 10 mg once daily for 14 days followed by 5 mg once daily for 28 days (or weight-based equivalent) and underwent all study procedures as specified in the original protocol, Amendment 1, and Amendment 2.
 
Part B includes all data obtained under Amendment 3 (dated 10 March 2016) during which subjects successfully completing Study PVO-1A-201 (including any subject who participated in Part A of Study PVO-1A-202) as well as up to 20 new adult subjects were followed for up to 24 months.
 
Part C includes all data obtained under Amendment 4 (dated 01 September 2017) and subsequent amendments during which subjects who participated in Part B will be followed for up to an additional 48 months. There will be no new subjects in Part C. Part C plus Part D total duration will not exceed 48 months.
 
Part D annual post last dose of study treatment assessments for up to 2 years will be obtained in subjects who were skeletally immature at the time of study treatment discontinuation in order to obtain longer-term safety data. No new subjects will be enrolled into Part D. Subjects will follow assessments as outlined in Table 4 for as long as they are not 100% skeletally mature. Part C plus Part D total duration will not exceed 48 months.
 
Non-Flare-up-based Treatment

---

## PROTOCOL SYNOPSIS

---

All subjects will receive non-flare-up-based treatment of 5 mg palovarotene once daily (weight-adjusted doses for skeletally immature subjects). Note: all weight-based dosing, both chronic and flare-up, will cease when subjects achieve  $\geq 90\%$  skeletal maturity based on hand/wrist radiography, but radiographic assessment of the growth plate (performed every 6 months) will continue until these subjects achieve 100% skeletal maturity defined as growth plate closure at both knee and hand/wrist locations. Additional radiographic assessments will be performed every 3 months in those subjects who (1) received the flare-up dosing regimen in the period of time since their last radiographic assessment; and (2) had not achieved 100% skeletal maturity on their last radiographic assessment.

Subjects will follow all assessments as outlined in [Table 1](#) and [Table 2](#). Subjects who cannot receive non-flare-up-based treatment will only undergo annual assessments (clinical laboratory tests will not be performed). In the event of a flare-up or traumatic event, these subjects will receive flare-up-based treatment and undergo all flare-up-based assessments, including clinical laboratory tests and radiographs if they have not reached 100% skeletal maturity.

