## PROTOCOL SYNOPSIS

- 10 mg for 8 weeks (56 days) once daily, for a total flare-up treatment duration of 12 weeks (84 days); 10 mg treatment may be extended if the flare-up is ongoing and continue until the flare-up resolves. Dosing will be extended in 4-week intervals and be based on clinical signs and symptoms as assessed by the Investigator.

Flare-up dosing will be weight-adjusted in subjects under the age of 18 years with less than 90% skeletal maturity on hand/wrist radiography at Screening. Note: all weight-based flare-up dosing will cease when subjects achieve  $\geq 90\%$  skeletal maturity based on hand/wrist radiography, but radiographic assessment of the growth plate will continue until these subjects achieve 100% skeletal maturity (defined as growth plate closure) at both knee and hand/wrist locations.

Flare-up-based dosing should also be initiated if the Investigator confirms the presence of a substantial high-risk traumatic event likely to lead to a flare-up.

Should a subject experience an intercurrent flare-up, or other substantial traumatic event likely to lead to a flare-up, at any time during flare-up-based treatment, the 12-week dosing regimen will restart upon new intercurrent flare-up or traumatic event confirmation by the Investigator (ie, 4 weeks of 20 mg palovarotene followed by 8 weeks of 10 mg palovarotene [or weight-based equivalent]). A Flare-up Cycle will include the first flare-up or traumatic event and any subsequent intercurrent flare-ups or traumatic events during the same dosing period. Flare-Up Cycle Safety Day 1 is defined as the first day that study drug is administered for the first flare-up or traumatic event during that cycle. Safety assessments will be performed at Flare-up Cycle Safety Day 1 and then every 12 weeks thereafter until treatment of the last flare-up or traumatic event in the cycle is completed. If any flare-up in a cycle has not resolved after 12 weeks, treatment and safety assessments will be extended and 10 mg palovarotene (or the weight-based equivalent) will be administered in 4-week intervals until all the flare-ups or traumatic events resolve and flare-up-based treatment has been completed. It is possible that subjects may experience more than one Flare-up Cycle during the study.

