In a study of Japanese versus non-Asian healthy volunteers, mean plasma concentrations after 5 and 10 mg palovarotene peaked at 4 hours post-dose for both subject populations; the mean terminal half-life ranged from 9.7 to 13 hours. Palovarotene was absorbed and eliminated in a similar manner for both populations, and pharmacokinetic parameters were similar at both dose levels based on geometric mean ratios and CIs for  $C_{max}$ ,  $AUC_{(0-\infty)}$ , and  $AUC_{(0-t)}$ .

Palovarotene was primarily metabolized by CYP3A4. Five metabolites, 6,7-dihydroxy (M1), 6-hydroxy (M2), 7-hydroxy (M3), 6-oxo (M4a), and 7-oxo (M4b) were observed for palovarotene in the clinical pharmacology studies. M1 was present in very low concentrations, usually below the limit of quantification (LOQ). Following administration of  $^{14}C$ -radiolabeled palovarotene, 97% of the dose was recovered in the feces and 3.2% in the urine. Overall, the metabolite profile was qualitatively similar to that reported in all the animal species.

In healthy subjects, palovarotene exposure at steady-state increased approximately three-fold with ketoconazole (a strong CYP3A4 inhibitor), decreased approximately 10-fold with rifampicin (a strong CYP3A4 inducer), increased slightly by 14% with prednisone (a weak CYP3A4 inhibitor), and did not change consistently with midazolam (a CYP3A4 substrate). Palovarotene did not impact the pharmacokinetics of concomitantly administered drugs, including oral prednisone and midazolam.

Co-administration of palovarotene with food resulted in a 40% increase in  $AUC_{0-\infty}$  and a 16% increase in  $C_{max}$  compared with administration under fasted conditions. Additionally,  $T_{max}$  appeared to be slightly shorter for fasted subjects dosed with palovarotene. Opening the capsule and sprinkling the contents onto soft food did not affect the PK of palovarotene. No clinically relevant differences in palovarotene pharmacokinetics were found between young males and elderly males and between elderly males and elderly females.

A population PK model was used to simulate palovarotene administration in pediatric patients in order to assess the appropriateness of weight-based dosing in skeletally immature children. The simulations identified weight-adjusted doses that provide derived steady-state exposures ( $AUC_{0-\tau}$ ,  $C_{max,ss}$ , and  $C_{min,ss}$ ) within the range of those for adults after receiving the 10- and 20-mg doses.

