## Palovarotene Safety

Consistent with other retinoids, the most commonly reported adverse events across all palovarotene dosing regimens in the FOP interventional studies were mucocutaneous and dermatologic events such as dry skin and lips, erythema, and pruritus. In general, the incidence, total number, duration and severity of mucocutaneous and dermatologic events increased with increasing palovarotene dose. These AEs generally resolved without sequelae after completion of palovarotene treatment. Musculoskeletal events such as arthralgia, pain in extremity, and condition aggravated (the Medical Dictionary for Regulatory Activities [MedDRA] preferred term used to capture reports of FOP flare-ups) were also commonly reported.

The majority of AEs in the palovarotene Phase 2 studies in FOP were mild or moderate in severity.

In the current study, and in the ongoing FOP Phase 2 study, subjects enrolled with open epiphyses undergo knee (anterior/posterior [AP] view) and hand/wrist radiographs (posterior/anterior [PA] view) for assessment of epiphyseal growth plate; and linear and knee height measurements for assessment of growth. The most common epiphyseal growth plate abnormality is growth recovery lines (dense metaphyseal lines) at both baseline and post-baseline time points. Potential premature closure of the epiphysis is closely monitored, and data are reviewed quarterly by an independent Data Monitoring Committee (DMC). Premature epiphyseal closure has been observed in subjects in the interventional FOP studies that have been reported as serious adverse events. Analysis of the SAEs suggests that the risk of premature epiphyseal fusion is higher in subjects with open epiphyseal growth plates who have received the flare-up dosing regimen. The finding of premature epiphyseal closure has been seen across all ages although the potential impact on growth is likely to be greater in the youngest, most skeletally immature subjects, given limitations in time to attain a greater percent of their final adult height.

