**Flare-up-based Treatment**

Subjects and/or their parents/caregivers will report potential flare-up symptoms to site personnel; such symptoms include, but are not limited to, pain, swelling, redness, decreased range of motion, stiffness, and warmth. Only one symptom is required to define a flare-up. If these symptoms are consistent with previous flare-ups, include a subject-reported onset date, and are confirmed by the Investigator as associated with a flare-up, subjects will immediately receive open-label palovarotene treatment as follows:

- 20 mg for 4 weeks (28 days) once daily. The first dose will be taken upon flare-up confirmation by the Investigator.

To be followed by:

- 10 mg for 8 weeks (56 days) once daily, for a total flare-up treatment duration of 12 weeks (84 days); 10 mg treatment may be extended if the flare-up is ongoing and continue until the flare-up resolves. Dosing will be extended in 4-week intervals and be based on clinical signs and symptoms as assessed by the Investigator.

Flare-up-based dosing should also be initiated if the Investigator confirms the presence of a substantial high-risk traumatic event likely to lead to a flare-up.

All dosing, be it non-flare-up or flare-up-based, will be weight-adjusted in subjects under the age of 18 years with less than 90% skeletal maturity on hand/wrist radiography at Screening ([Table 5](#)). Note: all weight-based dosing will cease when subjects achieve  $\geq 90\%$  skeletal maturity based on hand/wrist radiography, but radiographic assessment of the growth plate will continue until these subjects achieve 100% skeletal maturity (defined as growth plate closure) at both knee and hand/wrist locations.

The weight-adjusted palovarotene doses and dose de-escalation doses are:

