**Table 5. Weight-Adjusted Palovarotene Doses and Dose De-Escalation Doses**

Weight Range Category	20-mg Equivalent	15-mg Equivalent*	10-mg Equivalent	7.5-mg Equivalent*	5-mg Equivalent*	2.5-mg Equivalent*
20 to <40 kg	12.5 mg	10 mg	6 mg	4 mg	3 mg	1.5 mg

40 to <60 kg	15 mg	12.5 mg	7.5 mg	5 mg	4 mg	2 mg
≥60 kg	20 mg	15 mg	10 mg	7.5 mg	5 mg	2.5 mg

\* In the event of dose de-escalation from 20-mg, 10-mg, or 5-mg equivalent, respectively.

If the subject experiences intolerable side effects, the dose may be reduced to the next lower dose as shown in [Table 5](#); if the subject is already receiving the lowest possible dose, then study drug will be discontinued. In the event the subject required dose de-escalation due to an intolerable side effect for a previous flare-up, then the dose the subject will receive for a subsequent flare-up will be determined by the Investigator and the Medical Monitor. If there is evidence of partial or complete premature growth plate closure (with or without growth deceleration) study drug may be continued, interrupted, de-escalated, or discontinued. Dose modification decisions will be made by the Investigator upon review of the subject’s clinical and radiographic information, and following discussion of the risk/benefit with the subject/parent. The Investigator may also consult with the sponsor and the DMC.

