### **7.3.2 Knee and Hand/Wrist Radiographs**

Due to the potential for palovarotene to cause adverse effects on long-bone growth, all subjects at the time of enrollment into Study PVO-1A-202 with open epiphyseal growth plates at Screening had knee (AP view) and hand/wrist (PA view) radiographs.

For subjects from Part B continuing non-flare-up-based treatment into Part C with open

epiphyseal growth plates at the most recent assessment, knee (AP view, preferable on the left side) and hand/wrist (PA view, preferable on the left side) radiographs will be performed at the clinical site at Months 6, 12, 18, 24, 30, 36, 42, 48, 54, 60, 66 and 72.

For subjects from Part B starting non-flare-up-based treatment during Part C with open epiphyseal growth plates at the most recent assessment, knee (AP view, preferable on the left side) and hand/wrist (PA view, preferable on the left side) radiographs will be performed at Part C Screening. Subjects for whom radiographs were performed within the last 3 months will not need to repeat radiographs at Screening. Subjects with open epiphyseal growth plates at this assessment will also be evaluated at Months 6, 12, 18, 24, 30, 36, 42 and 48 at the clinical site.

Subjects who are skeletally immature at the time of study drug discontinuation and entering Part D (Y1 and Y2 post last dose of study treatment) will have follow-up knee (AP view) and hand/wrist radiographs (PA view, preferably on the left side) every year.

Additional knee and hand/wrist radiograph assessments will also be performed every 3 months ( $\pm 2$  weeks) in skeletally immature subjects who (1) received flare-up dosing in the period of time since their last assessment; and (2) had not achieved 100% skeletal maturity on their last assessment. The 3-month radiographic assessments will be performed at the clinical site unless the Investigator determines they can be performed at a local medical facility.

Once a subject has achieved 100% skeletal maturity (defined as closure of all assessed growth plates) as determined by the knee and hand/wrist radiographs, further radiographs will no longer be necessary. If 100% skeletal maturity is not achieved at both locations, then only the location that is still maturing would need to be monitored.

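### In PVO-1A-202, weight-adjusted dosing ends at 90% hand/wrist maturity with no exception for premature closure, and no passage says whether this rule or the premature-closure provisions govern

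*Protocol*

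**What the plan says.** **The rule that ends weight adjustment.** The PVO-1A-202 Synopsis (Non-Flare-up-based Treatment) says that "all weight-based dosing, both chronic and flare-up, will cease when subjects achieve" at least 90% skeletal maturity on hand/wrist radiography. The Synopsis text on flare-up treatment and both parts of Section 3.1 repeat the rule; the flare-up part reads "all weight-based dosing will cease when subjects achieve" the same threshold. None of the four statements has an exception. All four keep growth-plate radiographs going until full maturity is reached at both knee and hand/wrist, so they expect that some plates may still be open after the switch.

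**How maturity is defined.** The Synopsis gives "100% skeletal maturity defined as growth plate closure at both knee and hand/wrist locations". Section 7.3.2 gives "100% skeletal maturity (defined as closure of all assessed growth plates". Neither carries a qualifier for age or for premature closure.

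**What happens after premature closure.** The text below Table 5 in Section 3.1, repeated in Section 6.5, says that on "evidence of partial or complete premature growth plate closure (with or without growth deceleration) study drug may be continued, interrupted, de-escalated, or discontinued". The Synopsis (Assessments of Safety) has a similar provision. The investigator decides case by case and may consult the sponsor and the DMC. Section 6.5 adds that bone findings may require dose modification under the Bone Safety Management Plan (Section 7.3.3). Section 7.6 gives the DMC a role in recommending dose changes for treatment-related bone effects.

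**Why the doses are adjusted, and what the harm is.** Section 1.1.3.2 says of the pediatric modelling: "The simulations identified weight-adjusted doses that provide derived steady-state exposures" within the adult range. On the flare-up regimen, the safety text of the same section says: "Analysis of the SAEs suggests that the risk of premature epiphyseal fusion is higher in subjects with open epiphyseal growth plates who have received" that regimen. Section 3.2 treats premature closure as a serious identified risk.

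**The concern.** The trigger for leaving the weight-adjusted doses is a radiographic reading that the drug's main bone harm could itself move. If a subject's hand/wrist plates close early, the cessation rule followed literally takes that subject to the full doses without any change in weight. The premature-closure provisions address the same finding, and an increase is not among their listed responses.

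Two sites could therefore handle the same radiograph differently, each with text to support it. The subject concerned would already show the harm and might still have open knee plates.

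The threshold is in active use under this amendment. Section 7.7 requires hand/wrist and knee radiographs before restart in subjects aged 14 and over who were immature at their last assessment, and the Amendment 8 summary of changes says this is partly to establish whether weight-based dosing is needed.

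**Working it through.** The protocol gives no figure for the size of this switch, so there is none to reproduce. The inputs are the Table 5 doses and the 28-day plus 56-day flare-up course.

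**Step 1: does premature closure meet the trigger?** Full maturity means closure. Section 7.3.2 also says that once one location is fully mature, only the other need be monitored, so maturity is judged by location. A hand/wrist with every assessed plate closed is thus fully mature at that location and passes 90%, whatever the cause. For partial closure this is only an inference, because the protocol does not say how 90% is scored. Closure at the knee alone does not set off the rule.

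**Step 2: how large is the change?** Increase = 100 × (full dose ÷ weight-adjusted dose − 1).

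| Weight | 20-mg level | 10-mg level | 5-mg level |
|---|---|---|---|
| 20 to <40 kg | 20/12.5: +60.0% | 10/6: +66.7% | 5/3: +66.7% |
| 40 to <60 kg | 20/15: +33.3% | 10/7.5: +33.3% | 5/4: +25.0% |
| ≥60 kg | 0% | 0% | 0% |

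Over one 84-day flare-up course:

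- Full dose: 28 × 20 + 56 × 10 = 1120 mg.
- 20 to <40 kg: 28 × 12.5 + 56 × 6 = 686 mg; 1120/686 = 1.633, or +63.3%.
- 40 to <60 kg: 28 × 15 + 56 × 7.5 = 840 mg; 1120/840 = 1.333, or +33.3%.

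**Step 3: who can be reached?** Section 3.1 limits weight adjustment to subjects under 18 with less than 90% maturity, and says that children under 14 will not restart treatment. That leaves subjects aged 14–17 who are on drug, under 60 kg and previously below 90%. The protocol does not say how many there are.

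**Step 4: which text prevails?** The cessation rule is worded as mandatory. The premature-closure provisions are worded as permissive and give the decision to the investigator. Neither refers to the other, and no order of precedence is stated.

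**The case against.** The strongest reply is that the increase is not forced. The cessation rule is general, while the premature-closure provisions are specific to this finding, and a specific provision would ordinarily control. Under Section 7.3.2 the investigator receives every central radiograph reading. The Bone Safety Management Plan, which each site investigator signs, and the DMC add further control. The plan is not shown and may settle the matter. All of this stands, and it is why the point is a missing link between provisions. A reader might infer that the protocol flatly contradicts itself or compels a dose increase after closure. The documents do not support that: an investigator could use the discretion given to prevent the increase, and continuing the drug is itself a listed option.

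The affected group is also narrow. Section 7.7 describes subjects aged 14 and over as at or near adult height, with maturity of at least 90%, although the same section allows for some who are less mature. The 60–67% figures need a weight below 40 kg.

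It can also be said that limiting weight adjustment to immature subjects is a deliberate choice, and that mature subjects under 60 kg receive full doses by design. That is right, and a maturity-based cutoff is not in itself an error. The difficulty arises only when the maturity reading results from premature closure.

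What the reply does not supply is a statement that investigator discretion, the plan or a DMC recommendation overrides the mandatory sentence.

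**Conclusion.** The point holds as an unresolved overlap between a mandatory dosing rule and discretionary safety provisions. Followed as written, the cessation rule can raise the dose by 25–33% (40 to <60 kg) or 60–67% (20 to <40 kg) in a subject whose hand/wrist plates have closed prematurely, possibly with knee plates still open.

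This rests on two things: that complete hand/wrist closure is read as at least 90% maturity, which follows from the definitions; and that the unseen Bone Safety Management Plan does not already settle precedence, which cannot be checked here.

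Two wider readings are not supported. One is that any premature closure sets off the switch: knee-only closure does not, and for partial closure the text is silent on scoring. The other is that the point applies equally to PVO-1A-204: that protocol ends flare-up weight adjustment at age 18 and does not state the 90% hand/wrist rule.

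The passages should be reconciled because they bear on a serious identified risk and the change is cheap. The narrow population and the investigator's discretion keep this below a defect that must be fixed before the study can proceed.

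**What to change.** Reconcile the four statements of the cessation rule (Synopsis, non-flare-up and flare-up treatment; Section 3.1, both places) with the premature-closure provisions (Synopsis, Assessments of Safety; Section 3.1 below Table 5; Section 6.5) and with Section 7.3.3. The text should state which governs when a hand/wrist reading of at least 90% coincides with suspected or confirmed premature closure, or with an open knee plate. The sponsor and the DMC should make that decision; no dose or clinical rule is proposed here.

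The cost is amendment wording or a clarification letter, with no new procedures. The small downside is that some switches off weight-based dosing would need a documented decision instead of happening automatically.
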